7.2.4.2. Multiple Imputation

Multiple imputation with missing at random assumption will be used as an alternative method to handle missing data. The imputation method of choice depends on the type of missing data pattern:

- For data sets with monotone missing patterns, the variables with missing values will be imputed sequentially with covariates constructed from their corresponding sets of preceding variables. With IGA score (0-4) or EASI (0-72), a monotone method ([Rubin 1987](#)) with treatment group and stratification factors as predictors will be used.
- For data sets with arbitrary missing patterns, a fully conditional specification method ([van Buuren 2007](#)) that assumes the existence of a joint distribution for all variables will be used to impute IGA or EASI score.

After the missing values have been imputed, the binary variable IGA-TS or EASI75 response will be derived based on the definition specified in Section [7.2.1](#). The imputation will be repeated a number of times to generate corresponding complete data sets, in order to reflect the uncertainty around the true value. The proposed logistic regression described in Section [7.2.2](#) will be applied to each imputed datasets, and then the results will be combined for the inference.

7.2.4.3. Last Observation Carry Forward

For the participants who are missing postbaseline values, the last observed nonmissing value will be used to fill in missing values at Week 8. Then the proposed logistic regression described in Section [7.2.2](#) will applied to the imputed dataset.

7.2.4.4. Tipping Point Analysis

A tipping point sensitivity analysis will be conducted to examine the potential effects of missing data. The missing IGA-TS or EASI75 response at Week 8 in each treatment group will be replaced by a range of values to see how far we must change them for the results of the study to tip from significant to not. Between-treatment comparisons will be performed using a chi-square test.

7.3. Analysis of the Key Secondary Efficacy Parameters

7.3.1. Key Secondary Efficacy Measures

7.3.1.1. Itch Numerical Rating Scale Score

The Itch NRS is a once-per-24 hours ("daily") patient-reported measure of itch intensity assessed using an 11-point scale (0 = no itch to 10 = worst imaginable itch). Participants will be asked to record their highest (worst) level of itch in the evening over the 24-hour recall period.

The Itch NRS score for baseline will be determined by averaging the 7 daily NRS scores before Day 1 (Day -7 to Day -1). The by-visit Itch NRS score for postbaseline visits will be determined by averaging the 7 daily NRS scores before the visit day. If 4 or more daily scores are missing (out of the 7), the Itch NRS score at the visit will be set to missing.

The proportion of participants with a clinically relevant change in itch – defined as a ≥ 4 -point improvement in Itch NRS score from baseline to Week 8 – will be summarized by treatment groups for participants with baseline Itch NRS ≥ 4 .

7.3.1.2. PROMIS Short Form – Sleep Disturbance (8b)

The PROMIS Short Form – Sleep Disturbance (8b) is an 8-item questionnaire. Each item on the measure is rated on a 5-point scale with a range in score from 8 to 40 with higher scores indicating greater severity of sleep disturbance. The recall period will be the past 24 hours for the VC period and the past 7 days for the LTS period. The raw scores on the 8 items should be summed to obtain a total raw score. If 4 or more of the total items on the measure are missing for a given day/assessment, the scores should not be used.

For total raw score, the baseline will be determined by averaging the 7 daily scores on and before Day 1 (Day -6 to Day 1). The by-visit score for post-baseline visits will be determined by averaging the 7 daily scores before the visit day. If 4 or more daily scores are missing (out of the 7), the by-visit score at the visit will be set to missing.

Clinically meaningful difference is defined as a ≥ 6 -point change over baseline. The total raw score will be summarized by visit and by treatment. The proportion of participants with a ≥ 6 -point improvement in the PROMIS Short Form – Sleep Disturbance (8b – 24-hour recall) score will be summarized by treatment group for participants with baseline ≥ 6 .

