8.2.7. Patient-Reported Outcomes

Quality of life (QoL) will be assessed (see SoAs [Table 3](#) and [Table 4](#)) using the following tools: DQLI, PGIC, POEM, EQ-5D-5L, WPAI:SHP, Itch NRS, Skin Pain NRS, PROMIS Short Form – Sleep-Related Impairment (8a), and PROMIS Short Form – Sleep Disturbance (8b).

In order to avoid bias in the participants' responses to the questionnaires, all these assessments should be completed before any other evaluations or study procedures on the day of the study visit and prior to discussions with the investigator or study site staff.

At the baseline visit, all patient-reported outcomes must be completed before the participant's first study drug application.

Participants will be issued a paper questionnaire or hand-held device (eDiary) for daily assessments. The participant will be instructed to complete the diary during specific timepoints needed for each assessment beginning on the day of screening through Week 8 or treatment discontinuation. Detailed directions for the administration of an eDiary will be provided in the Study Manual.

Daily assessments will be performed by participants via a diary starting at the screening visit and all visits during the VC period:

- The participant will rate (during the past 24 hours) the following:
 - Itch NRS – the worst level of itch will be recorded in the evening.
 - Skin Pain NRS – the worst level of pain will be recorded in the evening.
 - PROMIS questionnaires:
 - Short Form – Sleep-Related Impairment (8a) will be completed in the evening.
 - Short Form – Sleep-Disturbance (8b) will be assessed in the morning.

Note: At Week 8 only (LTS baseline) for both PROMIS Short Form – Sleep-Related Impairment (8a) and Short Form – Sleep-Disturbance (8b), the “past 7-day recall” assessment will also be completed using the tablet during the site visit.

- Assessments to be completed during all VC site visits include the following:
 - EQ-5D-5L – starts at screening
 - WPAI:SHP – starts at screening
 - DLQI/CDLQI – starts at Day 1
 - POEM – starts at Day 1
 - PGIC – starts at Week 2

Assessments to be completed at the site during the LTS period (see SoA [Table 4](#) for timepoints):

- EQ-5D-5L
- WPAI:SHP
- DLQI/CDLQI
- POEM
- PROMIS Short Form – Sleep-Related Impairment (8a) and Short Form – Sleep-Disturbance (8b):
 - As stated above, this assessment will be completed during the LTS site visits (except for unscheduled visits) starting at Week 8.

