7.3.1.3. PROMIS Short Form – Sleep-Related Impairment (8a)

The PROMIS Short Form – Sleep-Related Impairment (8a) is an 8-item questionnaire. Each item on the measure is rated on a 5-point scale (1 = Not at all; 2 = A little bit; 3 = Somewhat; 4 = Quite a bit; and 5 = Very much) with a range in score from 8 to 40 with higher scores indicating greater severity of sleep-related impairment. The recall period will be the past 24 hours for the VC period and the past 7 days for the LTS period. The raw scores on the 8 items should be summed to obtain a total raw score. If 4 or more of the total items on the measure are missing, the scores should not be used.

For total raw score, the baseline will be determined by averaging the 7 daily scores before Day 1 (Day -7 to Day -1). The by-visit score for post-baseline VC visits will be determined by averaging the 7 daily scores before the visit day. If 4 or more daily scores are missing (out of the 7), the by-visit score at the visit will be set to missing.

Clinical meaningful difference is defined as a \geq 6-point change over baseline. The total raw score will be summarized by visit and by treatment. The proportion of participants with a \geq 6-point (clinically meaningful) improvement in the PROMIS Short Form – Sleep-Related Impairment (8a – 24-hour recall) score will be summarized by treatment group for participants with baseline \geq 6.

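### PROMIS 8b and 8a forms with 1 to 3 of 8 items unanswered are kept, but the only scoring rule is a raw sum, so responders near the 6-point threshold can be misclassified

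*SAP*

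**What the plan says.** SAP 7.3.1.2 describes 8b as "rated on a 5-point scale with a range in score from 8 to 40 with higher scores indicating greater severity of sleep disturbance". It gives one scoring operation: "The raw scores on the 8 items should be summed to obtain a total raw score". It gives one item-level missing-data rule: "If 4 or more of the total items on the measure are missing for a given day/assessment, the scores should not be used".

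SAP 7.3.1.3 uses the same sum for 8a with the same cut-off: "If 4 or more of the total items on the measure are missing, the scores should not be used". It also lists the item values: "1 = Not at all; 2 = A little bit; 3 = Somewhat; 4 = Quite a bit; and 5 = Very much".

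Daily totals become visit scores by averaging: "The by-visit score for post-baseline visits will be determined by averaging the 7 daily scores before the visit day". At least 4 of the 7 days are needed. The response rule is then applied to the raw total: "Clinically meaningful difference is defined as a ≥ 6 -point change over baseline".

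Under SAP 3.2, the 8b response is H14/H24, the last test in each Step 1 sequence, and the 8a response is H31/H32 in Step 2. All four are alpha-controlled. SAP section 1 applies the same plan to study INCB 18424-304.

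On data capture, Protocol 8.2.7 says: "Participants will be issued a paper questionnaire or hand-held device (eDiary) for daily assessments". Neither document requires every item to be answered.

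**The concern.** The cut-off at four missing items implies that forms with one, two or three unanswered items stay in use. Nothing says how their totals are adjusted. SAP 4.1.5 has no item-level rule. Nonresponder imputation does not help, because a kept partial form still yields a total and so is not a missing value.

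If the sum is programmed as written, an unanswered item adds 0, a value that no item on the scale can take. After baseline this looks like better sleep. At baseline it lowers the starting value and hides later improvement. There is also a discontinuity: three skipped items pull a day towards better sleep, while four remove the day.

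For POEM, DLQI and CDLQI (SAP 7.4.1.5 and 7.4.1.6) the plan says how one unanswered question is scored and rejects forms with two or more. On those scales 0 is a valid answer. PROMIS tolerates three of eight missing, has no zero category and gets no instruction, yet it is the instrument with alpha-controlled tests.

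At stake is who counts as a responder on two key secondary endpoints, in two trials.

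**Working it through.** **Inputs.** Eight items scored 1 to 5, up to 3 missing items tolerated, a 6-point threshold, and a mean of 7 daily totals with at least 4 days (SAP 7.3.1.2 and 7.3.1.3). The 1-to-5 values are explicit for 8a; for 8b they follow from the stated range.

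**The plan's own figure.** 8 × 1 = 8 and 8 × 5 = 40, which reproduces the stated range of 8 to 40.

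**One form with k items skipped.** The plain sum runs from (8 − k) × 1 to (8 − k) × 5. With no true change and equal item scores s, the artificial drop is k × s.

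| k skipped | Range of plain sum | Drop at s = 2 (true total 16) | Drop at s = 3 (true total 24) | Drop at s = 4 (true total 32) |
|---|---|---|---|---|
| 1 | 7–35 | 2 | 3 | 4 |
| 2 | 6–30 | 4 | 6 | 8 |
| 3 | 5–25 | 6 | 9 | 12 |

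One skipped item is worth at most 5 points, so it cannot create a response by itself.

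**The visit score.** If k items at score s are skipped on d of D usable days, the mean shifts by k × s × d / D. A full 6-point artefact needs d ≥ 6D / (k × s).

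- D = 7, two items at 3: 42/6 = 7, so all 7 days.
- D = 7, three items at 3: 42/9 = 4.67, so 5 days.
- D = 7, three items at 4: 42/12 = 3.5, so 4 days.
- D = 4, three items at 3: 24/9 = 2.67, so 3 days.

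A single day with three items at 3 skipped moves the mean by 9/7 = 1.29 points (7 days) or 9/4 = 2.25 (4 days). If that day falls in the Week 8 window, a true 5-point improvement scores as 6.29, a response.

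**Baseline skipping.** Take a true fall from 24 to 16, with one baseline item at 3 skipped every day. The plain sum gives 21 − 16 = 5, a nonresponse. Prorated, the baseline is 21 × 8/7 = 24 and the change is 8, a response.

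**Effect of prorating.** With no true change, total 24 and two items skipped, 18 × 8/6 = 24, so the artefact is 0. With equal item scores the same holds for one or three skipped items.

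**Illustrative simulation.** All inputs are assumed: mean item score 2.75 at baseline, random independent skips, and a mean improvement of 2 points (vehicle-like) or 6 points (active-like). Entries are response rates, complete data → plain sum.

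| Items skipped | 2-point group | 6-point group | Difference between groups |
|---|---|---|---|
| 5%, Week 8 only | 16.7% → 22.3% | 40.0% → 47.8% | 23.3 → 25.5 |
| 5%, baseline only | 16.5% → 11.0% | 40.5% → 30.9% | 24.0 → 19.9 |
| 10%, both times | 16.5% → 14.1% | 40.1% → 35.0% | 23.6 → 20.9 |

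The last row falls because equal random skipping scales both totals by about 0.9, so a true change of 6 reads as about 5.4. Prorated rates stayed within about 0.5 percentage points of complete-data rates in all scenarios. The table shows direction and rough size only, because the documents give no skip rate.

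**The case against.** The strongest reply is that the SAP never says a skipped item scores 0. It is silent on totals with one to three items missing. Totals of 5 to 7 would contradict its own range, and where it wants an unanswered question scored 0, as for POEM, it says so. A programmer might take the sum to require all eight answers. This stands in part: a zero score is the literal consequence of the text, not a stated rule. But requiring all eight answers would leave the four-item cut-off with no purpose, and either reading leaves a key secondary derivation to the programmer.

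Second, seven-day averaging dilutes isolated skips, and the device may force complete entry. Both points stand. The dilution is shown above. Completion checks may be set in the Study Manual, which is not available here. The paper option in Protocol 8.2.7 does not show that paper was used for PROMIS; it only means that complete entry cannot be assumed.

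Third, a reader might infer that skipped items push results towards success and that the artefact then travels through alpha recycling to a false claim of efficacy. The documents do not support this. Skips at baseline work the other way. The period is randomized and double-blind, and the scoring is the same in every arm, so with no treatment effect and similar skipping it produces no systematic difference between arms. H14 and H24 come last in their sequences, so they cannot affect earlier tests of the same dose. Step 2 opens only after all eight Step 1 hypotheses are rejected. Nothing in the documents points to skipping that differs by arm.

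**Conclusion.** The concern holds as a scoring gap. SAP 7.3.1.2 and 7.3.1.3 keep forms with 1 to 3 missing items, and the only operation given for them, a raw sum, can return totals below the scale minimum (as low as 5 against 8). Misclassification at the 6-point threshold can go in either direction, depending on whether items are skipped after or at baseline. It mainly concerns participants already near the threshold; a response made wholly of skips needs repeated multi-item skipping.

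The size depends on the item-skip rate, which is unknown, and is zero if all forms are complete. With similar skipping across arms the main harm is distorted response rates and lost precision. A spurious difference between arms would need differing skip patterns. The point should be settled because H14/H24 and H31/H32 are alpha-controlled, but the documents do not support calling it a threat to the trial's error control.

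**What to change.** In SAP 7.3.1.2 and 7.3.1.3, keep the rule that a form with 4 or more missing items is not used. Add that, with 5 to 7 items answered, total = (sum of answered items) × 8 / (number answered), calculated for each form before averaging over the 7 days, and applied equally to the 7-day recall forms. Make the change before unblinding, which SAP section 9 places after the primary database lock.

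The cost is one sentence in each of two sections and one line of derivation code, with no new data. If all forms are complete, no result changes. The small downside is the assumption that skipped items resemble the answered ones. Requiring all eight answers would also close the gap, but it discards usable days and makes the existing cut-off redundant.

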10.3. Type I Error Control

[figure not shown]
A graphical procedure with gatekeeping testing strategy for the primary and key secondary analyses will be implemented. The underlying procedure is derived using the methodology developed in Bretz et al (2009). This method will guarantee a strong control of the family-wise error rate.

Two families of 8 elementary hypotheses tests are grouped according to treatment comparison between each active dose group to vehicle, where

- Family 1 (1.5% BID vs vehicle):
 - H11: proportion of participants who achieve IGA-TS;
 - H12: proportion of participants who achieve EASI-75;
 - H13: proportion of participants with a ≥ 4 -grade improvement in Itch NRS over baseline;
 - H14: proportion of participants with a clinically meaningful improvement in the PROMIS Sleep Disturbance score.
- Family 2 (0.75% BID vs vehicle):
 - H21: proportion of participants who achieve IGA-TS;
 - H22: proportion of participants who achieve EASI-75;
 - H23: proportion of participants with a ≥ 4 -grade improvement in Itch NRS over baseline;
 - H24: proportion of participants with a clinically meaningful improvement in the PROMIS Sleep Disturbance score.

To control the overall Type I error rate, 2-sided $\alpha = 0.05$, the Bonferroni's method will be used. Within each family, the endpoints are tested in a fixed sequence at Bonferronized 2-sided $\alpha = 0.025$ level. The endpoint will be tested only if the associated primary (and secondary in previous steps) are rejected. For any dose level, if the 4 related null hypotheses can be rejected, then the fixed sequence for the other dose level can be conducted at 2-sided $\alpha = 0.05$ level. The approach can be visualized in [Figure 4](#).

Figure 4: Control of the Overall Type I Error Rate

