10.4.2. Secondary Analysis

Secondary efficacy analyses will be conducted in the ITT population. If the primary objective is achieved, the statistical comparisons for key secondary endpoints will be tested with the procedures specified in [Figure 4](#). The endpoints will be analyzed using the similar method as specified in the primary analysis.

All other secondary and exploratory efficacy variables will be summarized using descriptive statistics. For categorical measurements, summary statistics will include sample size, frequency, and percentages. Similar logistic regression models as specified in the primary and key secondary analysis will be used if applicable. For continuous measurements, summary statistics will include sample size, mean, median, standard deviation, standard error of the mean, minimum, and maximum. Continuous efficacy endpoints, including the actual measurement, change from baseline, and percentage change from baseline may also be analyzed by the mixed-effect model with repeat measurement.

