7.3.2. Key Secondary Efficacy Analysis

Key secondary efficacy analyses will be conducted in the ITT population in the VC period. If the primary objective is achieved, the statistical comparisons for key secondary endpoints will be tested with the procedures specified in [Figure 2](#). All of the key secondary endpoints will be analyzed using the similar logistic regression models as specified in the primary efficacy analysis.

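### The PROMIS responder filter of baseline 6 or more excludes no one with complete questionnaires on an 8-to-40 scale; a 6-point improvement needs a baseline of at least 14

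*SAP*

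**What the plan says.** SAP 7.3.1.2 describes 8b as eight items, each "rated on a 5-point scale with a range in score from 8 to 40 with higher scores indicating greater severity of sleep disturbance". Items are summed to a raw total. A day's form is discarded only if four or more items are missing, and no proration is stated. Baseline is a 7-day average. Response is a fall of at least 6 points, and the proportion of participants with that improvement in the 8b "score will be summarized by treatment group for participants with baseline ≥ 6".

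SAP 7.3.1.3 treats 8a in the same way, "with a range in score from 8 to 40 with higher scores indicating greater severity of sleep-related impairment", with the lowest item answer scored 1. It applies the same cut-off of 6: the 8a "score will be summarized by treatment group for participants with baseline" at or above that value.

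For itch, scored 0 to 10, SAP 7.3.1.1 says the proportion with at least a 4-point improvement "will be summarized by treatment groups for participants with baseline Itch NRS ≥ 4".

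The tests are described without any filter. SAP 7.3.2: "Key secondary efficacy analyses will be conducted in the ITT population in the VC period". Protocol 10.4.2: "Secondary efficacy analyses will be conducted in the ITT population". Protocol 10.3 words the 8b hypothesis for the higher dose as "H14: proportion of participants with a clinically meaningful improvement in the PROMIS Sleep Disturbance score". H24 in the Protocol, and H31 and H32 in SAP 3.2, likewise carry no baseline restriction. SAP 10.1 lists three departures from the Protocol, and this restriction is not among them.

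**The concern.** A baseline filter on a responder endpoint normally removes people who start too low to respond. The itch filter does that. The PROMIS filter sets the cut-off equal to the response threshold in the same way, but on a scale whose floor is 8, so the cut-off lies below every complete-form score. No inclusion criterion requires a minimum sleep score, so participants who cannot achieve a 6-point fall can enrol. They count as nonresponders in every arm.

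Four alpha-controlled hypotheses are involved. Under SAP 3.2, H14 and H24 are the last tests in each dose sequence. Failing one of them stops the other dose from being tested at 0.05. Step 2 (H31 and H32) opens only if every Step 1 hypothesis is rejected. Lost power on H14 or H24 therefore also affects what follows. SAP section 1 applies the same text to the twin study, INCB 18424-304.

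**Working it through.** **1. Scale range (the plan's own figure).** Eight items scored 1 to 5: 8 × 1 = 8 and 8 × 5 = 40. This reproduces the stated 8 to 40.

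**2. Does the filter exclude anyone?** The lowest 7-day mean of complete forms is 8.0. Since 8.0 > 6, no one with a complete-form baseline is removed.

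**3. Lowest baseline that allows a response.** Scale floor plus threshold: 8 + 6 = 14. The same rule for itch gives 0 + 4 = 4, which is the itch filter.

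**4. Incomplete forms.** With 1, 2 or 3 items missing and no proration, the lowest raw sum is 7, 6 or 5.
- A baseline mean below 6 is then possible, but only in extreme cases. Five days at 5 and two at 8 give (25 + 16)/7 = 5.86.
- A 5-item form after baseline could show a 6-point fall from a baseline of 5 + 6 = 11, purely because items are missing.
- Someone answering 2 on every item scores 16 on a complete form but 10 with three items missing. Prorated, 10 × 8/5 = 16.

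So 14 is exact for complete or prorated totals, not for raw partial sums.

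**5. Size of the dilution.** The documents give neither the share f below 14 nor any PROMIS response rate, so both are assumed. The 2:2:1 split of 600 gives 240 per active arm and 120 on vehicle. Alpha is 0.025 two-sided, as in SAP 3.2. Strata are not modelled. Let pA and pV be the response rates among those able to respond.
- Everyone in the denominator: rates pA(1 − f) and pV(1 − f), n = 240 and 120.
- Floor of 14: rates pA and pV, n = 240(1 − f) and 120(1 − f).

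Example by unpooled normal approximation, power = Φ(difference/SE − 2.241), for 35% vs 15% and f = 20%:
- Everyone: rates 28% and 12%; SE = √(0.28 × 0.72/240 + 0.12 × 0.88/120) = 0.0415; 0.16/0.0415 = 3.86; power 94.7%.
- Floor of 14: n = 192 and 96; SE = √(0.35 × 0.65/192 + 0.15 × 0.85/96) = 0.0501; 0.20/0.0501 = 3.99; power 96.0%.
- Loss: 1.3 points.

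The planned test is a Wald test from logistic regression (SAP 7.2.2 and 7.3.2). Exact enumeration of the Wald log-odds test gives these power losses in points:

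| Rates among those able to respond | f = 5% | 10% | 20% | 30% | 40% |
|---|---|---|---|---|---|
| 45% vs 15% | 0.0 | 0.0 | 0.1 | 0.4 | 1.4 |
| 35% vs 15% | 0.3 | 0.7 | 2.0 | 4.0 | 6.8 |
| 30% vs 15% | 0.9 | 1.2 | 3.1 | 5.2 | 6.5 |
| 40% vs 20% | 0.5 | 1.3 | 3.3 | 5.9 | 8.6 |

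For 35% vs 15%, Wald power is 96.2 / 94.8 / 90.8 / 84.6 / 75.3% with everyone counted, against 96.5 / 95.5 / 92.8 / 88.6 / 82.2% with the floor. The 20-point risk difference becomes 19 / 18 / 16 / 14 / 12.

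These ranges are not bounds. For example, 35% vs 20% with f = 10% gives Wald power of 69.5% against 71.7%, a loss of 2.2 points.

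**6. Type I error.** With 15% in both arms among those able to respond and everyone counted, the exact Wald error is 1.96% to 2.22% at nominal 2.5% over the same shares. It is not inflated.

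**The case against.** The strongest reply is that the dilution belongs to the Protocol's own design. Its hypotheses are unrestricted proportions tested in ITT, and SAP 7.3.2 repeats ITT. A filter that removes no one leaves the analysis matching the Protocol. Preferring participants able to respond over all randomized participants is a choice of estimand, and no section specifies a floor of 14. This stands: the filter does not cause the dilution; it only fails to remove it.

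The filter sentences also say what will be summarized, not what will be tested. A reader might infer that they were meant to define the test set for the four hypotheses, or that the value was copied from the itch rule. The parallel form makes a lapse likely, but the SAP gives no reason for the cut-off, so both readings are inferences.

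A bare cut-off of 14 would bring its own error. Because raw sums are not prorated, it would drop some participants only because items were missing, such as the one scoring 10 instead of 16. Simply deleting the filter is not complete either. Nonresponder imputation is defined for missing postbaseline values (SAP 4.1.5, 7.2.2 and 7.4.2.3), which leaves participants without a usable baseline with no stated rule.

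Finally, the power loss rests entirely on assumed inputs and may be negligible. None of this makes 6 a working cut-off on an 8-to-40 scale.

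**Conclusion.** The point holds for complete questionnaires. A cut-off of 6 excludes no one, the lowest baseline that allows a response is 14, and those from 8 to below 14 remain in the denominator of H14, H24, H31 and H32 under either reading of the text.

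The consequence is some lost power and a smaller reported risk difference. Across the four tabulated rate pairs, the Wald loss is about 0 to 1.3 points if 5% to 10% are below 14, and about 0.1 to 8.6 points if 20% to 40% are. Both the shares and the rates are assumptions. The knock-on effect on alpha recycling and entry to Step 2 is real in direction but has not been quantified.

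A reader might infer a bias between arms, an inflated false-positive rate or a weakened primary result. The documents support none of these: baseline is set before treatment can act, the rule treats all arms alike, and the primary endpoint and its stated power do not use PROMIS. The absence of the restriction from SAP 10.1 matters little while it excludes no one, but would matter once a working cut-off governs a test. Severity: minor to should-fix.

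**What to change.** Before unblinding, choose one of two routes.

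**Working filter.** In SAP 7.3.1.2 and 7.3.1.3, replace the cut-off of 6 with 14. Apply it to totals prorated to eight items (sum × 8 / items answered) when one to three items are missing, at baseline and after. State in 7.3.2 whether this set or all ITT is used for H14, H24, H31 and H32, and report the other as supportive. If the restricted set governs the tests, record that in SAP 10.1 as a departure from the Protocol's ITT hypotheses.

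Cost: SAP wording and one scoring rule. The denominator shrinks, from 228 vs 114 at 5% below 14 to 144 vs 72 at 40%, and the result describes participants able to respond, not all randomized. The floor is only the arithmetic minimum: someone at 14 must average the lowest possible score to respond.

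**No filter.** If the sponsor keeps the Protocol's ITT tests, delete the cut-off from both sections, report the set with baseline 14 or more as supportive, and state how participants with no usable baseline are counted. Cost: SAP wording only, but the dilution stays.
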